2 STUDY DESIGN

2.1 OVERALL DESIGN

For the PD cohort, participants will be recruited from Vanderbilt University Medical Center Neurology's Behavioral and Cognitive and Movement Disorder Clinics by Drs. [name] and [name]. We will prospectively enroll participants with idiopathic Parkinson's disease (n=50; age range=55-80 years), equally distributed and matched for age and sex between groups with (n=25) and without (n=25) mild

cognitive impairment. These populations provide a cohort to evaluate the potential relationship between glymphatic flow and beta-amyloid burden, given the elevated risk of beta-amyloid accumulation associated with PD and MCI conditions. Patients will have medical and motor presentation indicated for the community-based exercise program. Those patients with clinically-defined MCI, will be without evidence of vascular cognitive impairment, primary mood disorder, or comorbid medical condition that could contribute to cognitive symptoms (e.g. pulmonary, hematologic, metabolic, or vitamin deficiency). Potential participants will undergo a neurological and neuropsychological examination (including cognitive exam and behavioral/symptom questionnaires) to characterize their medical and neurobehavioral status. They will then undergo baseline neuroimaging protocols, both MRI brain scan (DTI-ALPS) and PET/CT (C11PiB) brain scan. Actigraph will be attached to the patient to continuously monitor motor activity. A background monitor of typing cadence will be activated on their computer to monitor for changes in fine motor control. The cohort will complete the same clinical and neuroimaging assessments after they participate in a 12-week community-based exercise intervention. Specifics about assessments and the exercise program are as follows.

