A.1.1.1. Clinical and neuropsychological examination. All potential participants will undergo baseline clinical and neuropsychological examination to determine eligibility, categorize MCI status, and provide quantification of neurocognitive functioning and neuropsychiatric symptomatology. The neuropsychological examination protocol will consist of memory measure (i.e., the Hopkins Verbal Learning Test – Revised [HVLT-R], consisting of Learning, Recall, and Recognition subcomponents). We will also administer three executive functioning measures (i.e., Trail Making Test – A & B57, Verbal Fluency [FAS], Stroop]), to facilitate exploratory analyses. To evaluate sleep disturbance symptomatology, PROMIS – Sleep Disturbance (SD) and Sleep-related Impairment (SRI) short forms will be administered.

A.1.1.2. PET. A single administration of approximately 370 MBq (10 mCi) Florbetapir 18F, then a 10- minute PET acquisition (2 × 5 minute frames) approximately 50 minutes later will be performed. Images will be reconstructed using an ordered subset estimation algorithm (4 iterations, 16 subsets, with a post-reconstruction Gaussian filter of 5 mm), and corrected for scatter and attenuation. Images will be co-registered to the high spatial resolution T1-weighted image as we have performed previously and a mean cortical:cerebellar SUVr will be calculated as the primary parameter of interest. For exploratory evaluation, we will also record SUVr in bi-temporal, bi-occipital, bi-frontal, and biparietal lobes.

A.1.1.3. MRI. The following imaging and angiography sequences will be completed. We will apply our previously reported 3T methods (16-channel neurovascular coil) with the below 50 min protocol:

Anatomical imaging. T1-weighted (MPRAGE; spatial resolution=1.0x1.0x1.0mm3; 3D turbo-gradient-echo; TR/TE=8.2/3.7ms), and T2-weighted (FLAIR; spatial resolution=0.9x1.1x3.0mm3; turbo-inversion-recovery; TR/TI/TE=11000/2800/120ms) imaging, and intracranial (spatial resolution = 0.5x0.8x1.4mm3; 3D gradient

echo; TR/TE=23/3.5ms) and extracranial (spatial resolution=0.9x0.9x3.0mm3 ; 2D gradient echo; TR/TE=18.6/3.2ms) time-of-flight (TOF) MR angiography (MRA).

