A.1.3. Statistical concerns. Statistical analyses will be overseen by statistician Co-I [name]. Descriptive statistics, including means, standard deviations, and ranges for continuous parameters, as well as percent and frequency for categorical parameters, will be presented. Tests for normality and homoscedasticity will be made. To test Hypothesis (1A), Pearson or Spearman (depending on normality findings) will be applied to evaluate the relationship between glymphatic flow, measured as the DTIALPS score, and the cortical:cerebellar SUVr, measured from PET. As an exploratory analysis to understand whether the relationship is spatially dependent, correlation testing will be repeated using the regional SUVr measures and corrected p-values reported. Power calculations are based on preliminary data in six MCI subjects in which an inverse correlation (Spearman's alpha =-0.49) was found between SUVr and DTI-ALPS score. With a sample size of 32, we should have 82% power to detect a correlation of -0.49 with two-sided p<0.05. To test Exploratory Hypothesis (1B), we will apply a Student's t-test or Wilcoxon rank-sum test (depending on normality findings), to evaluate whether mean glymphatic flow, measured as the DTI-ALPS score, is different between age- and sex-matched participants with vs. without MCI. Motivation is based on our preliminary data, where we have observed a large effect size (Cohen's d=2.3) in DTI-ALPS score between age- and sex-matched subjects with vs. without MCI.

A.1.4. Impact. Results will for the first time evaluate how the proposed human CNS lymphatic system and levels of beta-amyloid burden are altered in Parkinson's disease. If confirmed, results will motivate the use of evaluating human CNS lymphatic dysfunction with proposed methods for understanding betaamyloid clearance disorders.

A.2. Aims (2). Quantify the glymphatic functioning and beta-amyloid burden response to 12 weeks of a community-based exercise course developed specifically for PD patients.

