Patient heterogeneity is a concern. Since other clinical factors can affect brain and cognitive functioning, we plan to control for age and screen for the most common medical conditions that might disproportionally affect outcome assessments. Furthermore, we have selected an age-cutoff that reduces clinical heterogeneity and has extant support for the presence of our conditions-of-interest. Patient recruitment. Vanderbilt University Medical Center's Neurology division has a large clinical volume of adult patients with Parkinson's. Thus, our recruitment target is felt to be reasonable. Patient attrition. We have accounted for a possible 10% attrition/exclusion in our protocol. We will use compliance as a scalar variable, allowing us to retain all patients at follow up, regardless of degree of compliance.

C. Sex as a biological variable. Given the relative infancy of the field of human CNS lymphatic imaging, to our knowledge there is no literature reporting sex differences for all proposed biomarkers of the lymphatic drainage system. Therefore, we have powered our study to specifically address this concern, and subjects will be recruited equally for both sexes and statistical measures are in place to evaluate how each observable varies with biological sex. This should be the first study to report how these properties of the lymphatic system differ with biological sex in humans.

D. Scientific rigor and reproducibility. The need to understand CNS small blood and lymphatic vessels is becoming increasingly recognized, with more than 150 manuscripts published in the last five years on this topic. However, nearly all studies utilize animal models only, and there is much less information available on how this system operates in humans in health or in the presence of clearance disorders such as Alzheimer's disease. One reason for this is that reliable methods for evaluating lymphatics in vivo are underdeveloped. Methods proposed here (e.g., CVR compliance, lymphangiography, glymphatic flow, and CSF flow velocity)

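### The exploratory regional analysis in SAP A.1.3 tests each lobe's DTI-ALPS/SUVr correlation against zero, which does not test whether the lobes differ

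*SAP*

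**What the plan says.** SAP A.1.3 sets the test for Hypothesis 1A: "Pearson or Spearman (depending on normality findings) will be applied to evaluate the relationship between glymphatic flow" (the DTI-ALPS score) and the mean cortical:cerebellar SUVr. It then adds a regional analysis, whose purpose and method are given together: to "understand whether the relationship is spatially dependent, correlation testing will be repeated using the regional SUVr measures and corrected p-values reported".

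The regions are defined in SAP A.1.1.2, where "we will also record SUVr in bi-temporal, bi-occipital, bi-frontal, and biparietal lobes". Protocol section 2.2 (PET/CT) lists the same four lobes. Both documents call this use of the regional values exploratory.

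The power statement covers the global correlation only: "With a sample size of 32, we should have 82% power to detect a correlation of -0.49 with two-sided p<0.05".

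Neither document gives a test that compares the lobes, a region-by-DTI-ALPS interaction, an interval for a difference between correlations, or a rule for concluding that the relationship is or is not spatially dependent. The method behind "corrected p-values reported" is not named.

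**The concern.** The question and the test have different null hypotheses.

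- Question: is the correlation the same in the temporal, occipital, frontal and parietal lobes? The null is ρ1 = ρ2 = ρ3 = ρ4.
- Planned tests: is the correlation in this lobe zero? There are four separate nulls, ρj = 0.

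A multiplicity correction moves the threshold for the second set of hypotheses and does not turn them into the first. The prespecified p-values bear on spatial dependence only if someone reads significance in some lobes and not in others as a regional effect. That inference fails in both directions. With moderate power per lobe, a uniform relationship produces splits by chance. With high power, all four lobes can pass although their correlations truly differ. At stake is an unsupported statement about regional specificity, or a missed one.

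**Working it through.** **Inputs from the documents.** n=32, r=-0.49, two-sided 0.05 and 82% power (SAP A.1.3); four lobes (SAP A.1.1.2); n=50 as a sensitivity case (protocol 2.1). The -0.49 comes from six subjects.

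**Inputs that are assumed.** Correction by Bonferroni or Holm over four tests; correlation between lobar SUVrs of 0.6 to 0.95; multivariate normal data; the same true r in every lobe.

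**Step 1: the plan's own figure.** With Fisher's z, power = Φ(atanh(0.49)·√(n−3) − 1.96). Here atanh(0.49) = 0.536, √29 = 5.385 and their product is 2.887, so power = Φ(0.927) = 82.3%. The stated 82% reproduces.

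**Step 2: power per lobe after correction.** Bonferroni over four lobes gives 0.05/4 = 0.0125 two-sided, critical value 2.498. Power = Φ(2.887 − 2.498) = Φ(0.389) ≈ 65%. Each lobe therefore misses about 35% of the time even when nothing differs between lobes.

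**Step 3: how often a uniform relationship splits.** Simulation of DTI-ALPS and four lobar SUVrs (20,000 trials per setting), true r=-0.49 in all four lobes, counting trials with one to three lobes significant. Separate runs agree to about one percentage point.

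| Inter-lobe correlation | n=32 Bonferroni | n=32 Holm | n=50 Bonferroni | n=50 Holm |
|---|---|---|---|---|
| 0.6 | 54-55% | 31% | 27% | 11-12% |
| 0.8 | 38% | 18% | 19% | 7% |
| 0.9 | 27% | 10% | 14% | 4% |
| 0.95 | 19-20% | 5% | 10% | 2% |

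A test of equality of the four dependent correlations, applied to the same kind of data, rejects in about 4-5% of trials throughout.

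**Step 4: the reverse error.** With true correlations -0.8, -0.6, -0.6, -0.6, n=32 and inter-lobe correlation 0.8, a split appears in only 19% of trials (Bonferroni) or 8% (Holm). The equality test rejects in 81%.

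**Step 5: is -0.49 per lobe a fair setting?** The SAP's -0.49 refers to SUVr without a region. If each lobe has r=-0.49 and the lobes correlate at 0.6, the equally weighted lobe average has r = −(4 × 0.49)/√(4 + 12 × 0.6) = −1.96/3.347 = −0.59. Conversely, a lobe average of -0.49 puts each lobe at −0.49 × 3.347/4 = −0.41. At a common r of -0.40 (n=32, inter-lobe 0.6 to 0.9) the split rate is 56% to 28% (Bonferroni) or 39% to 12% (Holm), slightly higher than at -0.49.

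**Step 6: limits of the direct test.** With one lobe at -0.30 and three at -0.49 (n=32), its power is about 19% at inter-lobe correlation 0.6 and 38% at 0.8.

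**The case against.** A reader might infer that the plan will often report a uniform relationship as a regional one. The documents do not support that. The SAP says only that tests are repeated and corrected p-values reported; it never says that a split will be read as spatial dependence. Correlation testing also yields four coefficients, which a careful analyst could compare descriptively. Misreading is a risk created by the stated purpose, not a written decision rule.

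The size of the risk also rests on two quantities that the documents do not give. All four lobar values come from one PET scan, so a high inter-lobe correlation cannot be excluded. At 0.95 with Holm the split rate is about 5% at n=32, no worse than a nominal 5% test, and about 2% at n=50. Bonferroni gives clearly more splits than Holm.

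The analysis is labelled exploratory, has no numbered hypothesis, and regional SUVr is not among the endpoints in the protocol synopsis. The test and power of Hypothesis 1A do not depend on it.

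All of this stands and sets the level of the point. It does not remove the mismatch: exploratory status relaxes error control, but it does not make a test against zero answer a question about differences.

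**Conclusion.** The point holds as a minor, exploratory-level improvement. That the planned tests address a different null from the stated question follows from the text alone and needs no assumption. The size is conditional on a split being taken as spatial dependence, which the SAP does not prescribe. On that condition, a uniform r=-0.49 would mislead in 5% to 55% of trials at n=32, depending on the correction and the inter-lobe correlation, and in 2% to 27% at n=50. The risk is material at n=32 when the lobes correlate at 0.6 to 0.8 (18% or more under either correction) and small when they correlate very highly and a step-down correction is used. A reader might also infer that the main Aim 1 result is weakened; it is not, because Hypothesis 1A uses the single global SUVr.

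**What to change.** In A.1.3:

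1. Report the four regional correlations as estimates with 95% confidence intervals, and name the correction applied to any p-values.
2. Base any statement on spatial dependence on one test that the four dependent correlations, which share DTI-ALPS, are equal (Steiger or Meng-Rosenthal-Rubin type). If Spearman is used, take a patient-level bootstrap of the differences between coefficients instead; this variant was not simulated here. Report the differences with confidence intervals in either case.
3. State that significance in one lobe and not in another is not evidence of spatial dependence.
4. State that a non-significant equality test is not evidence of uniformity, given its low power for modest differences (Step 6 of the working).

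The cost is a few sentences in the SAP and a short analysis script on data already planned, with no added patients or procedures. The small downside is that regional claims become harder to make when lobes merely fall on either side of the significance threshold.

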1 STATISTICAL PLAN

1.1 AIM 1

Aim (1). To quantify the relationship between CNS lymphatic measures and beta-amyloid burden.

- Hypothesis (1A). Glymphatic flow and lymphatic collector velocity inversely correlate with beta amyloid measured from 18F-florbetapir PET in older adults with Parkinson's disease.
- Exploratory Hypothesis (1B). In Parkinson's subjects matched for age and sex, glymphatic flow and betaamyloid burden will be worse in patients with versus without mild cognitive impairment (MCI).

A.1.1 Experiment. We will enroll participants with idiopathic Parkinson's disease (n=32; age range=55- 80 years), equally distributed and matched for age and sex between groups with (n=16) and without (n=16) mild cognitive impairment. These populations provide a cohort to evaluate the potential relationship between glymphatic flow and beta-amyloid burden, given the elevated risk of beta-amyloid accumulation associated with both conditions. These patients will form a cohort to be assessed before and after a community-based exercise intervention. Participants will be recruited from Vanderbilt University Medical Center Neurology's Behavioral and Cognitive and Movement Disorder Clinics by Drs. [name] and [name]. Potential participants will undergo a neurological and neuropsychological examination to characterize their medical and neurobehavioral status. Patients will have medical and motor presentation indicated for the community-based exercise program. Those patients with clinically-defined MCI, will be without evidence of vascular cognitive impairment, primary mood disorder, Lewy body disease, or comorbid medical condition that could contribute to cognitive symptoms (e.g. pulmonary, hematologic, metabolic, or vitamin deficiency).

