Exploratory Hypothesis (2A). Exercise treatment will result in improved glymphatic functioning. Exploratory Hypothesis (2B). Exercise treatment will result in a reduction of cortical beta-amyloid uptake. Exploratory Hypothesis (2C). The degree of improvements in glymphatic functioning and cortical beta-amyloid uptake in response to exercise therapy will be more significant in MCI versus non-MCI participants. D.2.1 Experiment. We will enroll the patients from Aim (1) (A.1.) all of whom are undergoing community-based exercise intervention to treat symptoms of Parkinson's.

A.2.1.1. Exercise intervention procedure. Following baseline assessment, all patients will participate in a community-based kick boxing group exercise class designed for those living with Parkinson's called "Rock Steady Boxing." Patients will complete 12 consecutive, 90-minute, once-weekly classes, then undergo follow-up assessment. Treatment compliance will be monitored by the collaborating exercise trainer. All participants, regardless of degree of treatment compliance will receive follow-up assessment. *A.2.1.2. Imaging procedure.* PET and MRI methods as outlined in A.1.1.2. and A.1.1.3. will be performed.

A.2.2. Analysis and statistical plan. Our main hypotheses are that after 12 weeks of once-weekly exercise treatment for PD, glymphatic functioning (per DTI-ALPS) will improve and beta-amyloid burden (per PET) will decline. We expect that degree of treatment compliance standards will moderate these changes. We will also explore whether scalar degree of treatment compliance relates to degree of change in our assessment modalities. Statistical analysis will be overseen by statistics Co-I [name] and the same considerations outlined in Aims (1) will be applied. To test Exploratory Hypothesis (2A), a paired Student's t-test or Wilcoxon signed-rank test, depending on normality findings, will be applied to determine if glymphatic flow (DTI-ALPS score) is increased after, relative to before, exercise intervention. To test Exploratory Hypothesis (2B), an identical

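### Exploratory Hypothesis 1B compares groups matched on age and sex with an unadjusted test; adding age and sex to the model would cost almost nothing and could sharpen the estimate

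*SAP*

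**What the plan says.** Both documents build matching into the design. SAP A.1.1 describes participants as "equally distributed and matched for age and sex between groups with (n=16) and without (n=16) mild cognitive impairment". Protocol 2.1 uses the same description with larger groups: "equally distributed and matched for age and sex between groups with (n=25) and without (n=25". The hypothesis itself is framed for matched subjects: "In Parkinson's subjects matched for age and sex, glymphatic flow and betaamyloid burden will be worse in patients with versus without mild cognitive impairment (MCI".

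SAP A.1.3 gives the test for this hypothesis: "we will apply a Student's t-test or Wilcoxon rank-sum test (depending on normality findings), to evaluate whether mean glymphatic flow" differs between the matched groups. It names no covariate and no pair term. The rank-sum test is a test for independent samples. Where the SAP wants a paired analysis it says so, as for Hypothesis 2A: "a paired Student's t-test or Wilcoxon signed-rank test, depending on normality findings, will be applied to determine if glymphatic flow" rises after exercise. The 1B test is therefore read as unpaired and unadjusted.

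Two later statements bear on the point. SAP section B (on patient heterogeneity) announces control for age. Section C says that measures exist to examine variation by sex. Neither names a model or refers to 1B.

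No power or significance level is stated for 1B. Its motivation is preliminary: "we have observed a large effect size (Cohen's d=2.3) in DTI-ALPS score between age- and sex-matched subjects with vs. without MCI".

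**The concern.** When two groups are balanced on age and sex by design, these variables add little to the chance variation in the difference between group means. An unadjusted t or rank-sum test still counts their variance in its error term. If age and sex predict the outcome, the reported standard error then exceeds the true one, the confidence interval is wider than it need be, and the test rejects less often than 5% under the null.

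At stake is precision in an exploratory comparison: a moderate MCI difference could be missed, or reported with an unnecessarily wide interval. The plan also states an intention about age that no 1B analysis carries out.

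**Working it through.** **Inputs from the documents.** 16 per group (SAP A.1.1) or 25 per group (Protocol 2.1); the two must be reconciled, so both are used here. Preliminary d = 2.3 (SAP A.1.3). Two-sided 5% is stated for 1A and assumed for 1B.

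**Assumptions.** The share of within-group DTI-ALPS variance explained by age and sex (R²) is not given; the range 0 to 0.3 is shown. A smaller effect of d = 0.8, in units of the total within-group SD, is assumed for illustration.

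**Check on the plan's own figure.** There is no power figure for 1B to reproduce. The only one in A.1.3 is for 1A: "we should have 82% power to detect a correlation of -0.49 with two-sided p<0.05". With Fisher's z, Φ(atanh(0.49) × √(32 − 3) − 1.96) = Φ(0.536 × 5.385 − 1.96) = Φ(0.927) = 82.3%. It reproduces, but it does not bear on 1B.

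**Step 1: excess in the standard error.** With close matching, the true SE of the difference is √(1 − R²) times the SE that the unadjusted test uses. The ratio of reported to true SE is 1/√(1 − R²):

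- R² = 0: 1.00
- R² = 0.1: 1.05
- R² = 0.2: 1.12
- R² = 0.3: 1.20

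This ratio does not depend on the size of the MCI effect.

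**Step 2: type I error of the unadjusted t-test.** Simulation, 100,000 matched datasets per cell, 16 per group, with within-pair correlation equal to R²: 5.0%, 3.9%, 3.1% and 2.1% at R² = 0, 0.1, 0.2 and 0.3. A separate simulation with age matched within 0.2 SD and sex matched exactly gave 3.9%, 3.2% and 2.3% at R² = 0.1, 0.2 and 0.3, and 3.9%, 3.0% and 2.0% with 25 per group. The test is conservative throughout.

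**Step 3: power at the assumed d = 0.8.** Unadjusted power is simulated on matched data. Adjusted power is from the noncentral t with 2n − 4 degrees of freedom and noncentrality d√(n/2)/√(1 − R²). For n = 16, d√(n/2) = 0.8 × √8 = 2.263; dividing by √0.9 gives 2.385 and by √0.7 gives 2.704.

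| R² | 16 per group: unadjusted | adjusted | 25 per group: unadjusted | adjusted |
|---|---|---|---|---|
| 0 | 59% | 59% | 79% | 79% |
| 0.1 | 60% | 63% | 80% | 83% |
| 0.2 | 60% | 69% | 82% | 87% |
| 0.3 | 61% | 74% | 83% | 91% |

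Unadjusted power does not fall as R² rises. It fails to rise as adjusted power does.

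**Step 4: power at the plan's d = 2.3.** Noncentrality at 16 per group is 2.3 × √8 = 6.51, and power exceeds 99.9% with or without adjustment. At 14 per group, allowing for the SAP's 10% attrition, the unadjusted test still has 99.99%.

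**Step 5: where the loss could begin to matter.** The smallest d that the unadjusted t-test detects with nominal 80% power is 1.02 at 16 per group and 0.81 at 25 per group. The loss becomes material only if the true effect is around 1 or below and R² is about 0.2 or more.

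**Step 6: a paired test instead.** At R² = 0, d = 0.8 and 16 per group, a paired t-test has 56% power against 59% for the independent test, because it has 15 degrees of freedom instead of 30. The covariate model shows no such loss.

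**The case against.** The strongest reply is that nothing has been shown to be lost. The documents give no association between DTI-ALPS and age or sex, and SAP section C itself notes that sex differences have not been reported for all the proposed biomarkers. At R² = 0 the unadjusted test has the right size. At the only effect size that the plan gives for this comparison, power is effectively complete either way. Hypothesis 1B is exploratory, does not drive the sample size, and the error is on the safe side. All of this stands, and it keeps the point minor.

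A reader might infer that the standard error is in fact too large and that power is in fact lost. The documents do not support that; it depends on an unknown R². A reader might also infer that the matching is wasted. It is not: in an observational comparison, matching guards first against confounding by age and sex, and the unadjusted test keeps that protection. Only a possible gain in precision is forgone. Nor do the documents support the view that a paired test is required. They never say that individual pairs are formed, and their wording fits balance at group level equally well.

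The reply does not remove the case for adjustment. The d of 2.3 is preliminary and offered as motivation, the excess interval width does not depend on d, and the stated intention to control for age has no model behind it in 1B.

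**Conclusion.** The point holds as a minor, conditional one. The groups are matched on age and sex, the 1B test is unpaired and unadjusted, and the general statement about age is not carried into it. If age and sex explain 10% to 30% of DTI-ALPS variance (an assumption), the unadjusted standard error is about 5% to 20% too large and the true type I error at 16 per group is about 3.9% to 2%. At an assumed d of 0.8, the power forgone at 16 per group is then about 3 to 13 percentage points (63 − 60 and 74 − 61). If there is no association, or if the true effect is near 2.3, no power is lost. In no case is the false-positive rate inflated, so a positive 1B result is not put in doubt by this.

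**What to change.** In SAP A.1.3, replace the two-sample test for 1B by a linear model of DTI-ALPS on MCI status with age and sex as covariates, reporting the adjusted group difference with its 95% CI. If the normality check fails, use a bootstrap interval from the same model or a rank-based version. Apply the same model to the cortical:cerebellar SUVr, because 1B also names beta-amyloid burden but the stated test covers only DTI-ALPS. State whether matching is by group or by individual pair, and add a pair term only if pairs are actually formed.

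The cost is a sentence or two and two degrees of freedom (30 to 28 at 16 per group, 48 to 46 at 25 per group). No new data should be needed: age and sex are already matching variables. With no association, power is unchanged to the nearest percent (59% against 59%). The change also gives effect to the plan's statement about age, and it takes up imbalance left by imperfect matching or dropout.
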